3.10 SUBGROUP ANALYSES

Analysis for the primary efficacy endpoint will be provided for the following subgroups of baseline factors:

- Gender (male, female)
- Region (North America, Europe, Asia-Pacific, Other)
- Age group (<60 years, ≥60 years old)
- Baseline Cough Severity VAS (<60 mm, ≥60 mm)

A similar longitudinal ANCOVA model as that used for the primary efficacy endpoint will be utilized. For each subgroup, summary statistics including means and their 95% CIs will be provided for each intervention group at Week 12. For the subgroups with 15% or more of the FAS population across both intervention groups, the mean treatment differences (gefapixant - placebo) and their 95% CIs will also be provided at Week 12.

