9.10 Subgroup Analyses

Analysis for the primary efficacy endpoint will be provided for the following subgroups of baseline factors:

- Gender (male, female)
- Region (North America, Europe, Asia-Pacific, Other)
- Age group (<60 years, ≥ 60 years old)
- Baseline Cough Severity VAS (<60 mm, ≥ 60 mm)
- Potential co-morbid conditions associated with cough (ie, GERD, asthma, UACS)
Note: Details of the conditions will be provided in a separate sSAP.
- Concomitant medications (ie, antitussives and treatments for potential co-morbid conditions, proton pump inhibitors, inhaled corticosteroids first-generation anti-histamines). Note: Details of the concomitant medications will be provided in a separate sSAP.

A similar longitudinal ANCOVA model as that used for the primary efficacy endpoint will be utilized. For each subgroup, summary statistics including means and their 95% CIs will be provided for each intervention group at Week 12. For the subgroups with 15% or more of the FAS population across both intervention groups, the mean treatment differences (gefapixant - placebo) and their 95% CIs will also be provided at Week 12.

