3.6.2 Statistical Methods for Safety Analyses

Safety and tolerability will be assessed by clinical review of all relevant parameters including AEs, laboratory tests, and vital signs.

The analysis of safety results will follow a tiered approach (Table 2). The tiers differ with respect to the analyses that will be performed. Adverse events (specific terms as well as system organ class terms) and events that meet predefined limits of change in laboratory and vital signs are either prespecified as “Tier 1” endpoints, or will be classified as belonging to “Tier 2” or “Tier 3” based on the observed proportions of participants with an event.

Tier 1 Events

Safety parameters or adverse events of interest that are identified a priori constitute “Tier 1” safety endpoints that will be subject to inferential testing for statistical significance with p-values and 95% CIs to be provided for between-treatment differences in the proportion of participants with events; these analyses will be performed using the Miettinen and Nurminen (M&N) method (1985) [Miettinen, O. and Nurminen, M. 1985], an unconditional, asymptotic method. For this protocol, taste-related AEs (including dysgeusia, ageusia, hypogeusia, hypergeusia, and taste disorder) are considered Tier 1 events.

Tier 2 Events

Tier 2 parameters will be assessed via point estimates and 95% CIs provided for differences in the proportion of participants with events.

Membership in Tier 2 requires that at least 4 participants in any treatment group exhibit the event. The threshold of at least 4 events was chosen because the 95% confidence interval for the between-group difference in percent incidence will always include zero when treatment groups of equal size each have less than 4 events and, thus, would add little to the interpretation of potentially meaningful differences. Because many 95% confidence intervals for Tier 2 events may be provided without adjustment for multiplicity, the confidence intervals should be regarded as a helpful descriptive measure to be used in review, not a formal method for assessing the statistical significance of the between-group differences in adverse events and safety parameters that meet predefined limits of change.

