3.8 MULTIPLICITY

Other than an adjustment to the alpha level for the IA for efficacy, no multiplicity adjustment is planned.

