3.9 SAMPLE SIZE AND POWER CALCULATIONS

The sample size calculations are powered to test the primary efficacy endpoint, with the following assumptions based on the results from a phase 2 chronic cough study. In MK-7264 Protocol 012, the change from baseline in LCQ total score at Week 12 was 1.1 and 1.7 for 20 mg and 50 mg compared to placebo. In this study, given the population is targeted for participants with recent onset chronic cough (< 12 months) which is different from participants with chronic cough (\geq 12 months) in Protocol 012, conservative assumptions were used for sample size calculation:

- Treatment difference in change from baseline in LCQ total score at Week 12 is 1.1 point
- Common SD of change from baseline in LCQ total score is 3.5

Based on the assumptions above, a total of 414 participants (207 participants per intervention group) will provide at least 80% power. The calculation is based on an overall one-sided $\alpha=0.025$ significance level, adjusted for one IA for efficacy ($\alpha=0.001$), and one final efficacy analysis ($\alpha=0.024$). A dropout rate of 15% at Week 12 is accounted for the sample size calculation to ensure 352 evaluable participants complete the Week 12 evaluation.

With assumptions on the AE rates in the placebo group based on the Protocol 012 results, the minimum detectable AE rate differences are 8.4%, 9.0%, and 7.7% in overall taste-related AEs, oral paresthesia AEs, and oral hypoesthesia AEs, respectively.

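### The subgroup plan gives up to 10 unadjusted intervals for the LCQ difference but no estimate of how the treatment effect differs between levels

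*Combined protocol and SAP*

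**What the plan says.** sSAP 3.10 names four baseline factors for the primary endpoint: gender (2 levels), region (4), age split at 60 years (2) and baseline Cough Severity VAS split at 60 mm (2). That makes 10 levels. Every level gets arm means with CIs. For levels with at least 15% of the FAS, "the mean treatment differences (gefapixant - placebo) and their 95% CIs will also be provided at Week 12". The model is described only as similar to the primary longitudinal ANCOVA, and the sole interaction in that model (sSAP 4.1) is treatment by week.

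Protocol 9.10 plans the same output: "For each subgroup, summary statistics including means and their 95% CIs will be provided for each intervention group at Week 12", with differences under the same 15% rule. It lists six factors. The two extra ones, co-morbid conditions and concomitant medications, were removed in the sSAP by a logged change (sSAP Section 2), so the difference between the lists is not an error. Neither section names a treatment-by-subgroup term, test or between-level contrast.

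On multiplicity, sSAP 3.8 states: "Other than an adjustment to the alpha level for the IA for efficacy, no multiplicity adjustment is planned". sSAP 3.1 and protocol 9.1 give the reason, which is that the trial has a single hypothesis. For the unadjusted Tier 2 safety intervals, sSAP 3.6.2 adds that "the confidence intervals should be regarded as a helpful descriptive measure to be used in review, not a formal method". sSAP 3.10 has no matching sentence.

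**The concern.** A subgroup analysis of the primary endpoint asks whether the effect is consistent across levels. The quantity that answers this is the difference between the level-specific effects, with its own interval. The planned tables give the level-specific effects and leave that comparison to the reader.

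The common shortcut is to note which intervals exclude zero. That does not compare levels, because an interval can include zero simply because the level is small. The subgroup table could then be read as showing that gefapixant works in one gender, age group, region or severity band and not in another, with no planned estimate to set against that reading. What is at stake is the interpretation of the subgroup table. The primary conclusion is not at stake.

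**Working it through.** **Inputs.** From sSAP 3.9: "Treatment difference in change from baseline in LCQ total score at Week 12 is 1.1 point"; 15% dropout, leaving 352 evaluable (176 per arm at 1:1); one-sided alpha of 0.001 at the interim and 0.024 at the final analysis; and an SD of 3.5 for the change score. Levels and the 15% rule are from sSAP 3.10. The documents give no subgroup splits, so these are assumed and varied.

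**The plan's own figure.** sSAP 3.9 says "a total of 414 participants (207 participants per intervention group) will provide at least 80% power".
- Evaluable: 414 × 0.85 = 351.9, or 352.
- SE = 3.5 × sqrt(2/176) = 0.373, and 1.1/0.373 = 2.95.
- Power at one-sided 0.024 is 83.4%, so the statement holds.

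**Number of intervals.** 2 + 4 + 2 + 2 = 10 at most; 9 or 8 if one or two regions fall below 15%.

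**No true effect.** If the intervals were independent, the chance of at least one excluding zero would be 1 − 0.95^10 = 40.1% (1 − 0.95^8 = 33.7% for eight). They are not independent, since each participant falls in one level of every factor. I therefore use a simulation: 4,000 trials per scenario, 352 evaluable, normal Week 12 change scores, SD 3.5, factors independent of each other, 15% rule applied.

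| Assumed splits in % (gender; region; age; VAS) | Intervals | No effect: at least one excludes zero | Uniform 1.1: at least one factor discordant |
|---|---|---|---|
| 50/50; 25/25/25/25; 50/50; 50/50 | 10 | 33.3% | 92.5% |
| 30/70; 30/40/10/20; 60/40; 35/65 | 9 | 29.1% | 90.3% |
| 25/75; 35/45/10/10; 55/45; 30/70 | 8 | 25.9% | 86.6% |

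Discordant means that, within a factor, one level's interval excludes zero and another's does not. Other assumed splits gave up to 34% in the no-effect column and 90% to 93% in the last. Under no effect, the chance of at least one interval excluding zero in favour of gefapixant is 13% to 17%.

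**Why discordance is so common.** At a true effect of 1.1, the power within a level (two-sided 0.05) depends on its share of participants: 21% at a 15% share, 31% at 25%, 55% at 50%, 72% at 75%. For one two-level factor:
- 50/50: 2 × 0.55 × 0.45 = 49.5% discordant.
- 75/25: 0.72 × 0.69 + 0.31 × 0.28 = 58% discordant.

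Over four factors this accumulates to about 90%. Point estimates also scatter: at least one level shows a difference below zero in 18% to 27% of trials, although the true effect is 1.1 everywhere.

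**What an interaction estimate would give.** For a two-level factor with share p in one level, SE = sqrt(4 × 3.5²/(352p) + 4 × 3.5²/(352(1 − p))).
- p = 0.50: SE 0.75, 95% half-width about 1.5 points.
- p = 0.75: SE 0.86, half-width 1.96 × 0.86 = 1.7 points.
- At p = 0.50, power is 31% for an interaction of 1.1 points; 80% power needs (1.96 + 0.84) × 0.746 = 2.1 points.
- Four unadjusted tests at 5%: 1 − 0.95^4 = 18.5% chance of at least one false positive if independent (18% to 20% simulated).

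**The case against.** The strongest reply is that nothing confirmatory rests on these intervals. The trial has one hypothesis, the factors are prespecified, small levels are screened out, and no subgroup p-values or success rule are planned. Protocol Section 9 sends changes to non-confirmatory analyses to the sSAP, and two subgroup factors were dropped that way. All of this stands. It means that descriptive status is already implied, and that the missing label alone is only a missing detail.

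A second reply is that the discordance figures describe a reader's mistake. That is also fair: the plan never says to compare which intervals exclude zero. Nor is that the only possible reading. If the levels are fitted separately, a reader can form the between-level difference for a two-level factor with SE = sqrt(SE1² + SE2²), provided both levels are reported. This does not work for region when a level falls under 15%, and it leaves the key quantity to be rebuilt by hand.

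Three stronger readings are tempting and not supported:
- A reader might infer that a chance effect is likely when the drug does nothing. The figure is 26% to 34%, and only 40% even if all 10 intervals were independent.
- A reader might infer that each level gets its own separate model. The text says only that a similar model is used, which leaves a joint model open.
- A reader might infer that the 10-level count applies to protocol 9.10. It does not, because that section lists six factors.

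Finally, the remedy has limits. Interaction estimates here are imprecise, and four tests bring their own multiplicity.

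**Conclusion.** The concern holds as a minor, inexpensive improvement to the subgroup analysis. The plan omits the one estimate that shows whether the effect differs between levels. Without it, a drug that works equally in everyone would produce a discordant-looking table about 90% of the time, and a drug with no effect would show at least one interval excluding zero in about 26% to 34% of trials. The primary estimate, its type I error and its power are untouched.

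These sizes rest on the sSAP's 352 evaluable participants, SD of 3.5 and 1.1-point effect, on assumed subgroup splits, on independence between factors, and on a simple Week 12 comparison in place of the full longitudinal model. Baseline adjustment would narrow every interval somewhat if 3.5 is an unadjusted SD. The exact percentages are illustrative, but the pattern is stable over the splits tried.

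**What to change.** In sSAP 3.10, and in protocol 9.10 if it is amended:

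- For each factor, fit one longitudinal model in the full FAS. To the primary model add subgroup, subgroup by visit, treatment by subgroup, and treatment by visit by subgroup. Gender already has its main effect in the model.
- Report the Week 12 between-level difference in treatment effect with a 95% CI for gender, age and baseline VAS. For region, give a 3-df test, with fewer degrees of freedom if small regions are combined.
- State that consistency of effect is judged on these estimates and not on whether a given level's interval excludes zero.
- State that the level-specific intervals and the interaction results are unadjusted and descriptive, in line with the Tier 2 safety wording.

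The cost is a few sentences and four sets of contrasts, with no new data and no alpha. The downside is that most interaction results will be inconclusive. With four unadjusted tests an isolated positive is not rare either, so they should not be presented as formal tests of heterogeneity.

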3.11 COMPLIANCE (MEDICATION ADHERENCE)

For each participant, percent compliance will be calculated using the following formula:

$$\text{Percent Compliance} = \frac{\text{Number of Days on Therapy}}{\text{Number of Days Expected on Therapy}} \times 100\%$$

A day within the study will be considered an “on-therapy” day if the participant takes all required intervention as instructed in Section 8. When a participant takes less than or more than the required intervention on a day, that day is not considered an on-therapy day.

For participants who are followed for the entire study period, the “Number of Days Should be on Therapy” is the total number of days from the first scheduled intervention day to the last scheduled intervention day. For participants who discontinue from the study permanently, the “Number of Days Should Be on Therapy” is the total number of days from the first scheduled intervention day to the last dose day.

Summary statistics will be provided on percent compliance by intervention group for the APaT population.

3.12 EXTENT OF EXPOSURE

The duration of intervention for each participant will be evaluated by calculating the number of days on therapy. Exposure to study intervention will be summarized using descriptive statistics (mean, SD, median, minimum, and maximum) for the APaT population.

4. APPENDICES

4.1 Model Specification, Assumptions, and Sample SAS Implementation Codes for the Primary Efficacy Analysis

Model

Let Y_{ijt} denote the measurement for subject i , with treatment assignment j , at time t . Here $j = 0, 1$ represent Placebo and MK-7264 45 mg BID, respectively. Also, $t = 0, 1, 2$ represent Baseline, visits at Week 6 and 12, respectively.

The longitudinal ANCOVA model, that is, a mixed linear model will treat percent change from baseline in measurement, $(Y_{ijt} - Y_{ij0})/Y_{ij0}$, as the dependent variable, and adjust for the following independent variables:

- baseline measurement Y_{ij0}
- treatment (categorical variable with 2 levels, Placebo and MK-7264 45 mg BID)
- week (categorical variable with 2 levels, 6, 12)
- Gender (males and females)
- the interaction of treatment by week

Observations across subjects are assumed to be independent. Post-baseline measurements within the same subject are assumed to follow multivariate normal distribution with mean vector as specified above and an unstructured covariance matrix.

This longitudinal model provides valid statistical inference in the presence of possible missing data if the missing data mechanism is ignorable (or more specifically, MAR or MCAR). This missing data mechanism requires that the probability of a data point being missing does not depend on the missing data after adjusting for the observed data.

Reasons for discontinuation from the trial may include lack of efficacy, clinical or laboratory adverse experiences, relocation, withdrawal of consent, protocol deviations, and/or data processing issues. Missing data caused by relocation and data processing issues, are likely to be MCAR. On the other hand, missing data caused by discontinuation due to lack of efficacy may belong to MAR because the discontinuation may depend on the observed efficacy outcomes. The MAR or MNAR mechanisms might each underlie the other reasons to some extent. If treatment in large part determines the loss of data for these other reasons (such as clinical or laboratory adverse experiences), the mechanism may be close to MAR since treatment assignment is an observed variable and included in the analysis model. Based on the prior trial results, missing data due to other reasons is relatively infrequent.

Model Convergence

If the unstructured covariance matrix fails to converge with the default algorithm, then the AR(1) structure can be used to provide initial values of the covariance parameters.

Example SAS Codes

```
proc mixed data=adeff;
  where avisitn > 0;
  class subjid trt01p avisitn sex;
  model chg = base trt01p avisitn sex trt01p*avisitn/ solution notest;
  repeated avisitn / subject = subjid type=un;
  lsmestimate trt01p*avisitn 'MK at Week 12' [1, 1 2];
  lsmestimate trt01p*avisitn ' Placebo at Week 12' [1, 2 2];
  lsmestimate trt01p*avisitn 'Treatment Differences at Week 12' [1, 1 2] [-1, 2 2];
run;
```

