9 STATISTICAL ANALYSIS PLAN

This section outlines the statistical analysis strategy and procedures for the study. If, after the study has begun, but prior to any unblinding, changes are made to primary and/or key secondary hypotheses, or the statistical methods related to those hypotheses, then the protocol will be amended (consistent with ICH Guidance E9). Changes to exploratory or other non-confirmatory analyses made after the protocol has been finalized, but prior to unblinding, will be documented in a sSAP and referenced in the CSR for the study. Post-hoc exploratory analyses will be clearly identified in the CSR.

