9.4.1 Efficacy Endpoints

9.4.1.1 Primary Efficacy Endpoint

- LCQ total score measured as change from baseline at Week 12

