9.6.1 Statistical Methods for Efficacy Analyses

The analysis of efficacy endpoints will be based on the FAS population. Unless otherwise specified, all efficacy data from participants who have taken at least 1 dose of study intervention will be included in efficacy analyses.

Primary Efficacy Analysis

The LCQ is collected at baseline and after administration of the study intervention at Weeks 6 and 12. The primary efficacy endpoint of this study is the LCQ change from baseline in total score. The primary analysis approach will be conducted utilizing the longitudinal ANCOVA model. In this model, the response vector consists of the LCQ change from baseline in total score at each post-Baseline visit. The model will include factors for intervention group, visit, interaction of treatment by visit, gender, and the baseline LCQ score. The model will use all available LCQ change from baseline in total score at Weeks 6 and 12. Contrasts will be constructed to compare the Gefapixant intervention group to the Placebo group at Week 6 and Week 12. The least squares mean change from baseline with the associated standard errors will be displayed for each intervention group. Overall estimated treatment differences (Gefapixant – Placebo) along with corresponding p-values and 95% CIs will also be presented, with the exception of the primary efficacy endpoint, in which the CI width will be adjusted for an IA (Section 9.6). Further details of the model specification, assumptions, and SAS implementation codes will be provided in the sSAP.

Secondary Efficacy Analysis

The continuous secondary efficacy endpoints will be analyzed using a similar longitudinal ANCOVA model as used for the primary efficacy analysis. The model will include terms for intervention group, visit, interaction of treatment by visit, gender, and baseline score.

Table 4 summarizes the analysis strategy of the primary and secondary efficacy endpoints.

Table 4 Analysis Strategy for Primary and Secondary Efficacy Endpoints

Endpoint/Variable (at Week 12)	Statistical Method	Missing Data Approach
Primary		
Change from baseline in LCQ total score	Longitudinal ANCOVA	Model-based ^a
Secondary		
Change from baseline in Cough Severity VAS score	Longitudinal ANCOVA	Model-based ^a
ANCOVA=analysis of covariance; LCQ=Leicester Cough Questionnaire; VAS=Visual Analog Scale		
^a Includes data collected after early intervention discontinuation.		

The strategy for the IA is described in Section 9.7.

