1. INTRODUCTION

This supplemental SAP (sSAP) is a companion document to the protocol. In addition to the information presented in the protocol SAP which provides the principal features of confirmatory analyses for this trial, this supplemental SAP provides additional statistical analysis details/data derivations and documents modifications or additions to the analysis plan that are not “principal” in nature and result from information that was not available at the time of protocol finalization.

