3.6.1 Statistical Methods for Efficacy Analyses

The analysis of efficacy endpoints will be based on the FAS population. Unless otherwise specified, analyses will include all follow-up efficacy data collected for those participants who discontinued treatment.

Primary Efficacy Analysis

The LCQ is collected at baseline and after administration of the study intervention at Weeks 6 and 12. The primary efficacy endpoint of this study is the LCQ change from baseline in total score. The primary analysis approach will be conducted utilizing the longitudinal ANCOVA model. In this model, the response vector consists of the LCQ change from baseline in total score at each post-Baseline visit. The model will include factors for intervention group, visit, interaction of treatment by visit, gender, and the baseline LCQ score. The model will use all available LCQ change from baseline in total score at Weeks 6 and 12. Contrasts will be constructed to compare the Gefapixant intervention group to the Placebo group at Week 6 and Week 12. The least squares mean change from baseline with the associated standard errors will be displayed for each intervention group. Overall estimated treatment differences (Gefapixant – Placebo) along with corresponding p-values and 95% CIs will also be presented, with the exception of the primary efficacy endpoint, in which the CI width will be adjusted for an IA.

Secondary Efficacy Analysis

The secondary efficacy endpoint will be analyzed using a similar longitudinal ANCOVA model as used for the primary efficacy analysis. The model will include terms for intervention group, visit, interaction of treatment by visit, gender, and baseline score.

[Table 1](#) summarizes the analysis strategy of the primary and secondary efficacy endpoints.

Table 1 Analysis Strategy for Key Efficacy Endpoints

Endpoint/Variable (at Week 12)	Statistical Method	Missing Data Approach
Primary		
Change from baseline in LCQ total score	Longitudinal ANCOVA	Model-based ^a
Secondary		
Change from baseline in Cough Severity VAS score	Longitudinal ANCOVA	Model-based ^a
ANCOVA = analysis of covariance; LCQ = Leicester Cough Questionnaire; VAS = Visual Analogue Scale		
^a Includes data collected after early intervention discontinuation.		

Exploratory Efficacy Analysis

- **CSD Total Score**

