included in the primary analysis model. The random seed will be set equal to 72644243. This step will generate m monotone-missing datasets.

- 2) Applying parametric regression to the monotone-missing datasets, impute all the missing values. This will be accomplished for each treatment group using “proc mi” within SAS 9.3 or higher utilizing the option “monotone reg”, in conjunction with all of the covariates (excluding treatment) included in the primary analysis model. The random seed will be set equal to 72644243. This step will generate m complete datasets.
- 3) To implement the tipping-point aspect of the procedure, subtract a constant c from each of the imputed values of the active arms (to the detriment of active).
- 4) Analyze each of the post-imputation complete datasets using the primary model, obtaining point estimates for the mean of interest (e.g. change-from-baseline treatment difference at 12 weeks) and the associated variance.

Using “proc mianalyze” within SAS 9.3 or higher, the $m=100$ means and variances from the m analyses will be combined to obtain the final test statistic and p-value (Rubin, 1987). The final test statistic $\bar{Q} / (T^{-1/2})$ is approximately distributed as t_v , where \bar{Q} is the sample mean of the m treatment difference estimates, $T = \bar{U} + (m+1) (B/m)$, \bar{U} is the sample mean of the m variance estimates, and B is the sample variance of the m treatment difference estimates. The degrees of freedom, v , will be computed as follows [Barnard and Rubin, 1999]: $v = [(v_1)^{-1} + (v_2)^{-1}]^{-1}$, where $v_1 = (m-1) [1 + (\bar{U}/(1+m^{-1}) B)]^2$ and $v_2 = (1-\gamma) v_0 (v_0 + 1) / (v_0 + 3)$, with $\gamma = (1+m^{-1}) B / T$ and where v_0 represents the complete-data degrees of freedom .

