- 2) The imputation model is built, where, for each pattern of withdrawal, a predicted value model is created using the parameters estimated in Step 1. The random seed for the imputations is 72644243. For subjects in the control (reference) group, the predicted means are calculated under MAR assumption; for subjects in the other treatment arms, the predicted means are calculated under MNAR using the jump-to-reference approach, that is, the mean profile is based on the same treatment arm before withdrawal and ‘jumps’ to the mean profile based on the reference arm after withdrawal. A complete dataset will be generated using the imputation model for each set of the N=500 parameters obtained in Step 1.
- 3) For each of the imputed complete datasets, an ANCOVA model will be used for the change from baseline values at last time point. The model will include the same covariates as in the primary analysis model. The treatment difference across the 500 datasets will then be combined using PROC MIANALYZE, i.e., using Rubin’s rule for multiple imputation (Rubin, 1987) to provide the final results.

The J2R sensitivity analysis was implemented using macros developed by the DIA (Drug Information Association) Missing Data Working Group, which were available on page of www.missingdata.org.uk.

To get correct variance for the jump-to-reference imputation method, a pattern mixture model approximation will also be used. Based on the definition, the jump-to-reference imputation will have 0 mean treatment difference between treatment and control for those who dropped out in the treatment arm. Therefore, the overall mean treatment difference for jump-to-reference becomes

$$\theta^{J2R} = (\pi_t \mu_t^d + (1 - \pi_t) \mu_t^p) - \mu_t^p = \pi_t (\mu_t^d - \mu_t^p)$$

where π_t is the proportion of completers in the drug group, t is the last time point, and μ_t^d and μ_t^p are the mean effects for drug and control, respectively. It can be estimated from the primary analysis model as $\hat{\theta}^{J2R} = \hat{\pi}_t (\hat{\mu}_t^d - \hat{\mu}_t^p)$. The variance can be approximated by,

$$\text{var}(\hat{\theta}^{J2R}) = \hat{\pi}_t^2 \text{var}(\hat{\mu}_t^d - \hat{\mu}_t^p) + (\hat{\mu}_t^d - \hat{\mu}_t^p)^2 \hat{\pi}_t (1 - \hat{\pi}_t) / n$$

where n is sample size in the drug treatment arm. The first term can be estimated from the primary analysis model.

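### sSAP 4.1 specifies the primary model on percent change from baseline, but the protocol endpoint and the rest of the plan use change in LCQ points

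*Combined protocol and SAP*

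**What the plan says.** Protocol 9.4.1.1 gives the primary endpoint as "LCQ total score measured as change from baseline at Week 12", and sSAP 3.4.1.1 repeats it. The model text in protocol 9.6.1 and sSAP 3.6.1 agrees: "the response vector consists of the LCQ change from baseline in total score at each post-Baseline visit". Protocol 9.6.1 then hands over the detail: "Further details of the model specification, assumptions, and SAS implementation codes will be provided in the sSAP".

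The sSAP supplies that detail in appendix 4.1, under a heading that names the primary efficacy analysis. There, "a mixed linear model will treat percent change from baseline in measurement", and the formula printed beside it is (Yijt − Yij0)/Yij0. The example SAS code in the same appendix models a variable called chg, which neither document defines.

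Two further statements settle which text has precedence. Protocol 9 covers changes made after the study starts and before unblinding: if "changes are made to primary and/or key secondary hypotheses, or the statistical methods related to those hypotheses, then the protocol will be amended". sSAP 1 describes itself as a companion to "the protocol SAP which provides the principal features of confirmatory analyses for this trial" and limits its own changes to matters that are not principal. The sSAP change log (section 2) lists no move to percent change.

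**The concern.** Appendix 4.1 is the only place where the response of the confirmatory model is written as a formula, and programmers and validators will work from it. Its words and its formula both say percent change, so it cannot be read as a stray word.

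A programmer who followed it would test a different endpoint and report the result in percent instead of LCQ points. Participants with low baseline scores would carry more weight. The interim efficacy and futility analysis uses the same endpoint, and the secondary, CSD and subgroup analyses are described as using a similar model, so the ambiguity could spread. Two written scales for the single confirmatory test also leave a choice that could be challenged if it were made after the data are seen.

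**Working it through.** **1. The texts side by side**

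| Place | Scale of the response |
|---|---|
| Protocol 3, 9.4.1.1; sSAP 3.4.1.1 (objective, endpoint) | change from baseline |
| Protocol 9.1, 9.6.1, Table 4; sSAP 3.1, 3.6.1, Table 1 (model) | change from baseline |
| Protocol 9.1; sSAP 3.9 (sample size) | points: difference 1.1, SD 3.5 |
| sSAP 3.6.1, tipping point | primary model, with "change-from-baseline treatment difference at 12 weeks" as the example |
| sSAP 3.6.1, jump-to-reference imputation | "an ANCOVA model will be used for the change from baseline values at last time point" |
| sSAP 4.1, example code | chg (undefined; by naming convention, change) |
| sSAP 4.1, model specification | percent change, (Yijt − Yij0)/Yij0 |

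The documents never use the word absolute. It follows from the unqualified term change and from the effect and SD being stated in points.

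**2. The plan's own power figure**

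Inputs from protocol 9.9 and sSAP 3.9: 414 randomized, 15% dropout, one-sided alpha 0.024 at the final analysis. The difference of 1.1 and SD of 3.5 are from sSAP 3.9.

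- Evaluable: 414 × 0.85 = 351.9, so 352, or 176 per arm.
- Standardized effect: 1.1 / (3.5 × √(2/176)) = 1.1 / 0.373 = 2.948.
- Power: Φ(2.948 − 1.977) = Φ(0.971) = 83.4%.

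The claim of at least 80% is therefore true on the points scale. The documents give no effect or SD on the percent scale, so they imply no power for the model as 4.1 writes it.

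**3. What the formula does to a fixed gain**

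A 1.1-point gain as a percentage of baseline is 100 × 1.1 / baseline:

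| Baseline LCQ | 5 | 8 | 11 | 15 | 18 |
|---|---|---|---|---|---|
| Percent change | 22.0 | 13.8 | 10.0 | 7.3 | 6.1 |

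The same gain counts three times as much at 5 as at 15 (15/5 = 3).

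**4. Illustrative simulation**

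The baseline LCQ distribution is not in the documents. The assumptions are: baseline mean 10–12, baseline SD 2–3.5, a constant 1.1-point effect, change SD 3.5, scores held to the 3–21 range, one-sided alpha 0.024.

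| Model | Power, points | Power, percent | Loss (percentage points) | Trials where the scales disagree on significance |
|---|---|---|---|---|
| Week-12 ANCOVA, 176 per arm, slope of change on baseline 0 or −0.3, 3000 runs | 81–86% | 74–83% | about 1.5–12 | 3.3–15.8% |
| Two visits, unstructured covariance, 207 per arm, 15% missing at Week 12, slope −0.3, 1500 runs | 86–89% | 76–84% | about 1.5–12 | 4.5–15.0% |

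The two-visit model also assumes a residual correlation of 0.6 between visits and a Week 6 effect of 1.1 points. A separate Week-12 ANCOVA simulation (baseline mean 10 or 12, SD 2–4, 4000 runs) gave losses of about 2 to 9 percentage points and disagreement in about 5–12% of trials. On the percent scale the estimate reads about 9–12% where the points analysis targets 1.1.

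**The case against.** The strongest reply is that the documents already resolve the conflict. The protocol has precedence, a change of primary method needs an amendment, sSAP 3.6.1 states the response correctly, and the code beside the formula models chg. On this view 4.1 is a drafting slip, and harm requires someone to follow one sentence against everything else. The point about intent stands. It does not make the sentence harmless, because protocol 9.6.1 sends the reader to this specification and chg is never defined.

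The conflict with the sensitivity analyses is partial. The tipping-point analysis uses the primary model and mentions change from baseline only as an example, so it would inherit whichever scale the primary model has. The jump-to-reference approximation takes its mean difference and variance from the primary model, so it too would follow. Only the imputation version of jump-to-reference conflicts explicitly, and under 4.1 as written the two jump-to-reference calculations would be on different scales.

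The power loss depends on the assumed form of the effect. In reruns of the Week-12 ANCOVA with effect and residual spread both proportional to baseline, percent-scale power differed from points-scale power by about −4 to +2 percentage points. With only the effect proportional, the loss was about 4 to 24 points; a further check of other effect forms gave a loss of about 0 to 22. Low baselines drive the upper end. With a constant effect, mean 10 and SD 3.5, raising the baseline floor from 3 to 5 cut the loss from 12.3 to 6.1 points and left percent-scale power at 80.1%. The simulated loss is therefore illustrative and not a bound.

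**Conclusion.** The statement in sSAP 4.1 is wrong as written and must be corrected. It contradicts the protocol endpoint, the model text in both documents, the scale of the sample size and the jump-to-reference imputation model, and nothing in the amendment rule or the change log authorises a switch. Change in LCQ points governs.

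This conclusion rests on the texts and needs no simulation. The sample size is sound: 83.4% power on the intended scale. If 4.1 were followed, the trial would test a different quantity in different units with no documented power. The illustrative loss of about 1.5 to 12 percentage points assumes a constant 1.1-point effect and the baseline distributions listed above. In those runs percent-scale power was above 80% throughout at baseline SD 2 and below 80% throughout at SD 3.5, with some values within simulation error of 80%. A fall below the planned 80% is possible but not established.

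**What to change.** In sSAP 4.1, define the dependent variable as change from baseline, Yijt − Yij0, and delete the word percent and the division by Yij0. Beside the example code, state that chg is the absolute change in LCQ total score, in points. Record the correction in the sSAP summary of changes before unblinding.

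The cost is one corrected line, one definition and one log entry. No new data, extra analysis or protocol amendment is needed, because the protocol already specifies this scale.
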